### **8.3. Exclusion Criteria**

1. Admitted to an intensive care unit (ICU).
2. Females who are pregnant, lactating, or planning to become pregnant during the study. Female patients of childbearing potential will take a pregnancy test at the intervention visit and will be excluded if pregnant.
3. Inability (e.g. dysphagia) to or unwilling to swallow capsules.
4. Known or suspected toxic megacolon and/or known small bowel ileus.
5. Bowel obstruction or other gut motility issues occurring in the last two weeks that are unresolved as noted by the patient or in the EMR.
6. Major gastrointestinal surgery (e.g. significant bowel resection) within 3 months before enrollment not including appendectomy or cholecystectomy.
7. History of bariatric or colectomy surgery.

8. Concurrent intensive induction chemotherapy, radiation therapy, or biologic treatment for an active malignancy. Patients on maintenance chemotherapy may be enrolled after consultation with the medical monitor.
9. Expected life expectancy <6 months.
10. Patients with severe anaphylactic or anaphylactoid food allergy.
11. Solid organ transplant recipients ≤90 days post-transplant or on active treatment for rejection.
12. Neutropenia ( $\leq 500$  neutrophils/mL) or other severe immunosuppression. Anti-TNF will be permitted. Patients on monoclonal antibodies to B and T cells, glucocorticoids, antimetabolites (azathioprine, 6-mercaptopurine, methotrexate), calcineurin inhibitors (tacrolimus, cyclosporine), and mycophenolate mofetil may only be enrolled after consultation with the medical monitor.\*
13. At risk of CMV/EBV associated disease, negative IgG testing for cytomegalovirus (CMV) or Epstein Barr Virus (EBV).
14. Any other gastrointestinal illness including diarrhea.
15. On oral vancomycin or metronidazole.
16. Having been taking the currently prescribed antibiotic for over 72 hours.
17. On an antibiotic treatment anticipated to exceed 19 days.
18. Having received an FMT by any route in the 90 days prior to enrollment.
19. Any condition that would jeopardize the safety or rights of the patient, would make it unlikely for the patient to complete the study, or would confound the results of the study.

\*Patients enrolled into the trial do not need to be checked for neutropenia. When considering whether a patient meets inclusion/exclusion criteria, conditions commonly causing neutropenia should be only enrolled at the discretion of the medical monitor. Such conditions include, but are not limited to, chemotherapy, chronic idiopathic neutropenia, Kostmann's syndrome, leukemia, myelofibrosis, and sepsis.

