#### **5.6.4. Risk Minimization**

As stated in section 5.6.2, we will ensure patients know the signs of infection and know who to contact if they develop an illness during the study period. Additionally, we will administer the capsules under direct supervision while the patient is in the hospital. Subjects' tolerance for consuming capsules will be established at enrollment visit by giving them an inert size 00 capsule.

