### **7. STUDY DESIGN AND ENDPOINTS**

#### **7.1. General Design**

This is a phase II, double-blind, randomized, placebo controlled trial assessing the effects of either daily (group 1) or one-time (group 2) oral FMT on the composition and function of the gut microbiome compared to placebo (group 3) in a population of patients with a history of CDI currently on antibiotics for a reason other than current CDI. Participants will be 18 years of age or older, have 72 hours or less of an antibiotic and meet all inclusion criteria while having no exclusion criteria prior to randomization. Patients will be randomized at a 1:1:1 ratio using permuted blocks (block size=10). Randomization will be double-blinded. Each subject (n=30) will be followed for 6 months. Stool samples will be taken at baseline and every 3 days  $\pm$  1 day from all subjects regardless of treatment group while the patient is hospitalized. If/when a patient is discharged from the hospital, the patient will continue to provide stool samples every three days during FMT. Following completion of the FMT intervention, the patient will provide stool samples once weekly for the 1 month follow-up period. All patients will be asked to complete a patient diary to report diarrhea history.

Up to one gram of stool will be sent to Finch therapeutics for additional 16s rRNA sequencing.

**Intervention:** There are 2 intervention groups for this study. Both groups will receive oral FMT capsules from OpenBiome for the prevention of CDI during antibiotic treatment. All patients will fast (clear liquids only) for a minimum of 2 hours prior to administration and 1-hour post-administration for the daily groups and be fasting for 8 hours prior and 1 hour post FMT consumption for the single dose group. The capsules will be administered in the patient's room while admitted or in the ID clinic or CRU if the patient is an outpatient and the first dose will occur under direct observation. Patients admitted to the hospital as well as all patients in the single dose group will be observed for 30 minutes post-administration to ensure the capsules are safely consumed. Hospitalized patients need to be observed 30-minutes post-administration following only the first dose. As mentioned above, the oral FMT capsules will be administered in two ways:

**Group 1:** This group will receive daily oral FMT capsules. Five capsules will be administered each day of the

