### **8.2. Inclusion Criteria**

1. Cognitively intact and willing to provide informed consent.
2. Willing and able to comply with all study procedures for the duration of the study.
3. Able to take oral medications.
4. Age 18 or over.
5. Recent CDI episode occurring in the last 90 days with completion of therapy as confirmed by the electronic medical record (EMR)
6. Receiving antibiotics at enrollment for reasons other than CDI and having taken the antibiotics for no longer than 72 hours.
7. Women of childbearing potential in a sexual relationship with men must use an acceptable method of contraception (including, but not limited to, barriers with additional spermicidal foam or jelly, intrauterine devices, hormonal contraception started at least 30 days before enrollment into the study, or intercourse with men who underwent a vasectomy) for 4 weeks following completion of the study treatment.
8. Males must agree to avoid impregnation of women during and for 4 weeks following completion of the study treatment.
9. Able to take the test capsule successfully with no signs or symptoms of dysphagia.\*

\*For patients not receiving treatment during the enrollment visit, the ability to successfully swallow the test capsule can be confirmed the day the intervention is administered.

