#### *Enrollment: Will take place in a clinical setting*

All patients with a history of CDI on antibiotics for any reason other than CDI meeting the eligibility criteria will be eligible for enrollment. Eligibility will be confirmed during the enrollment visit. Patients admitting with CAP and UTIs will be preferred. A detailed consent process will be administered by study staff who are trained in consenting procedures. Potential participants who fulfill the eligibility criteria will undergo a detailed clinical assessment by the research team which will include demographics, medical history, dietary

information and current medication. Data from this assessment may be from the participant/substitute decision maker, healthcare team and/or medical record.

- Data points at enrollment study visit:
  - General parameters:
    - Date of birth
    - Sex
    - Smoking status
    - Race
    - Ethnicity
    - Highest level of education
  - Past medical history and allergies
    - A focused collection of past medical history (including common infections)
  - Current medication list
    - Current antibiotic use, including dose
  - Dietary history
  - Social history
    - Alcohol, smoking history
  - Recent hospitalizations
  - Exposure to farm animals
  - Recent international travel history
  - Examination findings
    - Vital signs: temperature, height, weight, heart rate, blood pressure, O2 saturation if on chronic oxygen therapy. (Vital signs measurements at all time points may be abstracted from medical records if available.)
    - Relevant review of symptoms
  - Overall assessment of current health
  - Stool consistency (Bristol Stool Scale) and frequency
- Sample collection
  - Stool sample collected using a stool collection kit/hat and provided with patient diary
- Formal aspects
  - Informed consent procedure
  - Verification of inclusion and exclusion criteria including administering 'test' capsule and documenting:
    - Safe to receive intervention (yes/no)
    - Able to swallow test capsule (yes/no)

Immunocompromised patients at risk for CMV/EBV will have blood drawn for the EBV and CMV antibody test done by the UWHC lab. The blood draw will be done by a UWHC phlebotomist or their local lab if this is preferred by the patient. All costs will be covered by the study. Results will be released to the patient and included in their medical record.

*Baseline (Day 0): Will take place in a clinical setting*

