**Figure 2. Donor eligibility workflow for an international public stool bank**

## 17. APPENDIX II

### 17.1. Study Schematic

## 17.2. Study Calendar

	Screening	Enrollment/ Baseline Visit*	Daily for Duration of Antibiotic regimen +7 days	Every 3 days (+/-1 day) from Enrollment to intervention end	Follow- up Calls	48-72 hours post Antibiotic Completion*	7 Days Post Antibiotic Completion	Unscheduled Visit*	Weekly Post-FMT Follow-Up Sample Collection 	1 Month Post-FMT Call	6 month Post-FMT assessment
Verification of Inclusion and Exclusion Criteria	X	X									
Invited to participate	X										
Informed Consent		X									
Pregnancy test		D 				S 					
Test Capsule		D				S					
CMV/ EBV PCR testing		X 									
Vitals Collection	X					S		X			
Physical Exam	X					S		X			
Clinical Symptoms Assessment		X			X	S		X	X	X	
Dietary Assessment		X			X	S	D	X			X
Risk Factor Assessment		X									
Demographics collection		X									
Medical History		X									X
Concomitant Medications		X			X	S	D	X	X	X	
FMT or Placebo Administration		D	D			S	D				
Stool Sample Collection		X		X	X	S	D		X		
Antibiotic Resistant Bacteria Testing		X		X		S	D		X		
Patient diary	X	X	X	X	X	X	X		X		
Post-ingestion Observation		D				S					
Adverse Events Assessments		D			X	S	D	X		X	X

X-Indicates all groups

D-indicates daily dosing groups (Groups 1 and 3) only

S-indicates single dose group (Group 2) only

\*Indicates a clinic visit

Lasts a duration of 4 weeksWomen of childbearing potential only Patients at risk of CMV/EBV associated disease only

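### The pregnancy test and test capsule are timed by treatment arm, so Group 2 patients can be excluded on an entry criterion days to weeks after randomization, with no rule for analysing them

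*Combined protocol and SAP*

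**What the plan says.** **The general rule.** Section 7.1 says participants must "meet all inclusion criteria while having no exclusion criteria prior to randomization", and Section 8.1 repeats the requirement.

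**Pregnancy test.** Section 8.3, item 2: "Female patients of childbearing potential will take a pregnancy test at the intervention visit and will be excluded if pregnant". No arm is named.

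**Test capsule.** Passing it is inclusion item 9 in Section 8.2. The footnote adds that, for patients not treated at the enrollment visit, "the ability to successfully swallow the test capsule can be confirmed the day the intervention is administered". In practice that means Group 2. Two other places put it at enrollment for everyone. Section 5.6.4 says "Subjects' tolerance for consuming capsules will be established at enrollment visit by giving them an inert size 00 capsule", and the enrollment visit in Section 11.1 lists "Verification of inclusion and exclusion criteria including administering 'test' capsule and documenting", with no distinction by arm.

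**Study Calendar (17.2).** Both checks are coded D in the enrollment/baseline column and S in the column for 48-72 hours after antibiotics. The legend reads "D-indicates daily dosing groups (Groups 1 and 3) only" and "S-indicates single dose group (Group 2) only".

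**Randomization.** The schematic in Section 3 puts it on Day 1, after the Day 0 baseline. Section 11.1 (Baseline, Day 0) has Groups 1 and 3 eligible for dosing at baseline according to their randomized assignment.

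**Analysis.** Section 9.8 names intention-to-treat, in a paragraph on incomplete doses. Section 12.2 aims at eight per group who complete treatment and are analysed. Section 8.6.2.1 lists pregnancy among the reasons for withdrawal and keeps all randomized subjects in the safety analysis.

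**The concern.** An eligibility criterion should decide who is randomized. Here two criteria can remove a patient afterwards, and when they can do so depends on the assigned arm. Groups 1 and 3 are checked at about Day 0; Group 2 is checked once antibiotics have ended. Three things are at stake.

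- **Comparability.** Over the interval between baseline and its dosing visit, Group 2 is exposed to eligibility exclusions that the daily arms no longer face. Its patients meanwhile give stool every three days (Sections 7.1 and 11.2), which is the primary-outcome material of Section 7.2.1. A patient can contribute primary data and then be excluded on an entry criterion.
- **No analysis rule.** Nothing says whether such a patient stays in the microbiome comparison. Intention-to-treat and an analysis of completers give different answers.
- **Feasibility.** Section 7.2.2 asks whether patients are willing and able to take the capsules and wants retention by group. A swallowing failure found before randomization is a screening failure. Found at Group 2's dosing visit, it could be counted as an exclusion, a retention loss or a feasibility failure.

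**Working it through.** **1. The plan's own figure.** Section 12.2 enrolls 10 per group to leave 8. The implied loss is (10 - 8)/10 = 20%, and 8/(1 - 0.20) = 10 per group, or 3 x 10 = 30 in total, as stated. This is consistency of arithmetic only, since Section 12.1 says the sample size was not set by a hypothesis test.

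**2. Do the passages fit together?**

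| Check | Before randomization or at enrollment, all arms | On dosing day, or by arm |
|---|---|---|
| Pregnancy test | 7.1 and 8.1 (general rule) | 8.3 item 2; 17.2 (D and S) |
| Test capsule | 7.1 and 8.1 (general rule); 5.6.4; 11.1 Enrollment | 8.2 footnote; 17.2 (D and S) |

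For Group 2 the two columns cannot both be followed. For Groups 1 and 3 the order is uncertain. Section 3 places randomization on Day 1, after baseline. The Day 0 text in 11.1, however, doses these groups by their randomized assignment, and a calendar entry that applies to certain groups can be followed only once the group is known.

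**3. Delay from randomization to the Group 2 checks.** Patients enter 0-3 days into antibiotics (72-hour limit, Section 8.2), and Group 2 is dosed 2-3 days after the course ends. For a course of L days:

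- shortest delay = L - 3 + 2
- longest delay = L - 0 + 3

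| Course (assumed) | Delay |
|---|---|
| 5 days | 4-8 days |
| 7 days | 6-10 days |
| 14 days | 13-17 days |

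With stool due every three days, 4/3 to 17/3 gives roughly one to five scheduled post-baseline samples before the checks.

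**4. Size of the loss.** One exclusion is 1/10 = 10% of an arm and 1/2 of the two-patient allowance (10 - 8 = 2). The documents give no failure rate, so p is assumed. For 10 patients:

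- P(at least 1) = 1 - (1 - p)^10
- P(3 or more) = 1 - P(0) - P(1) - P(2), binomial with n = 10. Three losses are needed to fall below eight.

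| Assumed p | At least 1 | 3 or more |
|---|---|---|
| 2% | 18% | 0.09% |
| 5% | 40% | 1.2% |
| 10% | 65% | 7.0% |

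**The case against.** **Group 2 may not be alone.** A reader might infer that only Group 2 can lose randomized patients on an eligibility criterion. The documents do not establish this. Section 8.3 sets the pregnancy test at the intervention visit for every woman of childbearing potential. The D coding and Day 0 dosing by assignment suggest that Groups 1 and 3 may also be checked after allocation, just before their first dose. Only the Day 1 entry in Section 3 points the other way. This stands: what is certain is a difference in delay. If all arms are checked after allocation, the conflict with Section 8.1 is wider, not smaller.

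**Blinding.** A reader might also infer that the timing of the checks breaks the blind. It does identify Group 2, but that group is already recognizable: no capsules during antibiotics, then a single 30-capsule dose for which Sections 7.1 and 9.1 describe no matching placebo. The checks do not separate daily FMT from daily placebo, which share a schedule, and moving them would not restore any masking. Blinding is a separate matter from this point.

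**Late failures may be rare.** The test-capsule footnote is permissive, inclusion item 3 and exclusion item 3 already screen for difficulty swallowing, and the pregnancy test covers only women of childbearing potential in a population expected to be half female. Nothing in the documents anchors rates of 2-10%, and the allowance absorbs one or two losses. This also stands and limits the size of the point.

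**Existing safeguards.** The plan names intention-to-treat and keeps all randomized subjects in the safety analysis. That helps, but the efficacy set is undefined and Section 12.2 looks to completers, so the gap remains.

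**Conclusion.** The point holds as a defect in the timing of eligibility checks. Followed as its calendar is written, the plan checks two entry criteria at arm-dependent times. In Group 2 that is about 4 to 17 days after randomization for assumed courses of 5 to 14 days, and after primary-outcome stool samples have been given. This contradicts Sections 7.1 and 8.1 and, for the test capsule, Section 5.6.4 and the enrollment visit in 11.1. No rule says how a late failure enters the efficacy analysis.

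The numerical effect is modest and rests on assumed failure rates. At least one loss in an arm of ten is plausible (18% to 65% across the assumed range), but falling below eight for this reason is unlikely (at most 7.0%). No loss of power can be quoted, because the plan has no power calculation. The change is worth making because excluding randomized patients on entry criteria is avoidable and cheap to avoid.

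**What to change.** - Reconcile Sections 3, 5.6.4, 7.1, 8.1, 8.2 (footnote to item 9), 8.3 (item 2), 11.1 (Enrollment and Baseline) and 17.2 so that both eligibility checks are completed before randomization in every arm, and state the day of randomization relative to baseline and first dose consistently.
- In the calendar, show both checks at enrollment for all groups. Do not remove the dosing-day checks already scheduled for Group 2.
- State in Sections 12.2 and 12.3 that a patient found at a later check not to meet a criterion remains in the intention-to-treat efficacy analysis as randomized.
- Report patients who were randomized but not dosed, by arm and with the reason, and say how they count toward feasibility and retention.

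Any decision about dosing after a later check is for the sponsor. The cost is wording plus a few extra pregnancy tests, for women of childbearing potential in Group 2, who would be tested at enrollment as well as at the dosing visit.

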## **8.4. Subject Screening and Retention**

### ***8.4.1. Subject Identification***

Potential subjects will be identified by the study team who has access to a list of patients admitted to UWHC for infectious diseases that is updated daily. The medical monitor will screen these patients' EMR to determine eligibility. Once potential subjects meeting the eligibility criteria are identified, the treatment team's physician or nurse will ask the patient if he/she is interested in hearing about the study and if so, will introduce the research team. The patient will be invited to hear about the study and, if interested and meeting all eligibility criteria, participate in the study. As patients with community acquired pneumonia (CAP) and urinary tract infections (UTIs) are likely to be on shorter antibiotic courses, initial recruitment will focus on these patients. We, however, do not plan to limit to just CAP and UTI patients and will consider patients admitted to other non-ICU acute care units or outpatients with anticipated short courses (2 weeks or fewer) of antibiotic treatment.

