After the baseline clinical assessment and stool sample have been collected, subjects in groups 1 and 3 (daily FMT and daily placebo) are eligible to undergo administration of the intervention (DE or placebo) in

accordance with the randomization schedule. The intervention will be administered by the blinded treatment staff and the participant observed for 30 minutes following administration. Post-ingestion observation of inpatients will only occur after the first dosing; subsequent inpatient dosing will be administered by a study physician/nurse but do not require 30 minutes of observation. Pre-intervention vital signs (as previously described) will be collected or abstracted from the medical record prior to first dose. Participants will be provided with information regarding monitoring for minor and severe adverse event related to the intervention administration. Participants will be encouraged to report any concerning symptoms to staff. Oral nutrition may commence 1 hour post-capsules administration. Study staff do not need to collect a blood sample to check for neutropenia prior to dosing.

For all patients, a baseline stool sample will be collected and all patients should begin to fill out their patient diary starting on Day 0. If a patient is unable to provide a stool sample, peri-rectal swabs may be collected.

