### *Group 1 (daily FMT) and Group 3 (daily placebo): Will occur in a clinical setting for inpatients.*

Capsules will be delivered to the patients every day by a blinded member of the treatment team during the time they are admitted. If the patient is discharged or an outpatient, he/she will be provided with enough capsules to complete the study and will be asked to consume 5 capsules per day while on antibiotics as well as for 7 days post-antibiotic treatment completion. Outpatients and patients discharged during the follow-up period will be called or emailed (depending on patient preference) weekly to remind them to take their capsules as well as to send in their stool samples every three days (+/- 1 day). The researcher calling the subject will also ask the subject to count the number of pills he or she has remaining (recorded in the patient diary) and ask about any adverse events or changes to medications and diet. Study staff do not need to collect a blood sample to monitor for neutropenia. If the subject has any capsules remaining after completion of study intervention (e.g. missed doses, shortened antibiotic course after study intervention has been dispensed), the subject will be asked to return the remaining capsules to the Infectious Disease Research lab.

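### Exclusion 12 sets its neutrophil limit per mL, which is 0.5 per microliter, so recorded counts of 10 to 500 per microliter do not meet it; check the unit and correct it

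*Combined protocol and SAP*

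**What the plan says.** The combined protocol and SAP, Section 8.3, item 12, excludes neutropenia, with a limit of 500 or fewer "neutrophils/mL) or other severe immunosuppression". The rest of the item permits anti-TNF agents and allows several other immunosuppressants after consultation with the medical monitor.

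The footnote to Section 8.3 states that "Patients enrolled into the trial do not need to be checked for neutropenia". It adds that "conditions commonly causing neutropenia should be only enrolled at the discretion of the medical monitor", with an open-ended list of such conditions. Section 11.1, Baseline (Day 0), says "Study staff do not need to collect a blood sample to check for neutropenia prior to dosing". Section 11.2 says of the daily groups that "Study staff do not need to collect a blood sample to monitor for neutropenia", and repeats this for the single-dose group. None of these places gives a neutrophil number.

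Eligibility of the listed inpatients is judged from the chart. Section 8.4.1 says "The medical monitor will screen these patients' EMR to determine eligibility". Section 8.3, item 19, is a general safety exclusion that begins "Any condition that would jeopardize the safety or rights of the patient".

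**The concern.** A limit of 500 cells per mL is 0.5 cells per microliter. At that level the numeric part of the exclusion catches almost no one: a charted count of 10, 100 or 500 per microliter lies above it. If the limit was meant per microliter, it is 1000 times too low as written.

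This is an operative eligibility limit in a trial that gives human fecal microbiota, and Section 5.6.1 lists fever and bacteremia among the reported risks of FMT. The trial can enroll patients in whom a low charted count is plausible. Items 8 and 12 allow maintenance chemotherapy, antimetabolites, calcineurin inhibitors and mycophenolate after consultation with the medical monitor, and Section 8.4.2.1 names transplant clinics as a recruitment source. Because the study draws no count of its own, no later laboratory value would expose a misapplied limit.

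**Working it through.** **Inputs**

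- Limit as written: 500 or fewer neutrophils per mL (Section 8.3, item 12).
- Conversion: 1 mL = 1000 microliters.
- Counts required by the protocol: none at enrollment (Section 8.3 footnote), before dosing (Section 11.1) or in follow-up (Section 11.2, all three groups).
- Where a count could come from: the existing medical record (Section 8.4.1).

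The protocol derives no figure on this point, so there is no calculation of its own to reproduce. The check is a unit conversion.

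**Step 1. The written limit per microliter**

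500 per mL / 1000 microliters per mL = 0.5 per microliter (0.0005 x 10^9/L).

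**Step 2. Example counts against the written limit**

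Count per mL = count per microliter x 1000. Ratio = count per mL / 500.

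| Count per microliter | Count per mL | Ratio to written limit | Meets 500 or fewer per mL | Meets 500 or fewer per microliter |
|---|---|---|---|---|
| 0.5 | 500 | 1 | yes | yes |
| 10 | 10,000 | 20 | no | yes |
| 100 | 100,000 | 200 | no | yes |
| 500 | 500,000 | 1000 | no | yes |
| 1000 | 1,000,000 | 2000 | no | no |

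The lower end of 10 per microliter is only illustrative. Every count above 0.5 per microliter fails the written limit.

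**Step 3. The limit if per microliter was meant**

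500 per microliter x 1000 = 500,000 per mL = 0.5 x 10^9/L. Ratio to the written limit: 500,000 / 500 = 1000.

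**Step 4. Does any other text supply the right number?**

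The Section 8.3 footnote, Section 11.1 and both parts of Section 11.2 mention neutropenia without a limit. The figure in item 12 is the only one, so nothing in the document corrects it.

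**The case against.** The strongest objection is that the point rests on one letter. The text reviewed was machine-read, and a micro sign could have become an m. Where mL appears in Appendix 16.1, it shows only that a genuine mL is read correctly. No micro sign appears elsewhere in the text, so its extraction cannot be tested. This stands, and it is why the correction depends on checking the source.

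Second, no passage states that per microliter was meant. It is an inference, and the sponsor has to confirm it.

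Third, other safeguards overlap. A patient with a low charted count can be excluded as severely immunosuppressed under item 12 itself, under item 19 or, where they apply, under items 8 and 11. The Section 2 summary also lists severe immunocompromise as a main exclusion. Conditions that commonly cause neutropenia go to the medical monitor, who also screens the charts of listed inpatients. A wrong enrollment would require that monitor to apply 0.5 per microliter literally and to pass over every other route. This stands too, and it keeps the practical effect small. It does not make the number right. The other routes depend on judgment or on a named condition, and the footnote is triggered by a condition, not by a low count. An unexplained low count in the chart is the case a numeric limit should settle without discretion.

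Finally, the ratios of 20, 200 and 1000 all come from one conversion factor. They describe the unit label and do not measure patient risk.

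**Conclusion.** The concern holds as stated. As written, the only numeric neutrophil limit in the protocol is 0.5 per microliter, and charted counts of 10 to 500 per microliter do not meet it. If per microliter was intended, the limit is too low by a factor of 1000.

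Two assumptions remain open: that the source PDF prints mL, and that the sponsor meant per microliter. Neither can be settled from the text reviewed, so confidence is medium.

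The exclusion as a whole still works through its non-numeric parts, and a careful medical monitor would probably exclude a severely neutropenic patient. There is no effect on endpoints, randomization, sample size or analysis. The unit should be corrected because this is a safety limit and should not rely on readers silently repairing it.

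**What to change.** 1. Compare the unit in Section 8.3, item 12, with the source PDF.
2. If it prints mL, ask the sponsor to confirm that per microliter was intended. If so, restate the limit as 500 or fewer neutrophils per microliter (0.5 x 10^9/L).
3. If the PDF already prints per microliter, leave it unchanged.

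The cost is one unit in one criterion. Study procedures, sample size and analysis stay as they are.
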